7.6. Translational Research

Blood and/or bone marrow aspirates will be collected at various times, throughout the study in order to support research aimed at understanding the biological effect of GSK2879552 alone or in combination with azacitidine in MDS as well as identifying indicators of sensitivity or resistance. Specifically, the evaluation of responders, responders at relapse, and non-responders for DNA methylation, gene alteration status, cell surface marker expression and/or pathway activation may lead to the discovery of potential new diagnostic markers or novel drug combinations. Similarly, pre- and on-treatment blood and bone marrow specimens will be evaluated for target engagement, therapeutic response, and/or evaluated for changes in gene expression; thus supporting identification of a biologically effective dose and furthering our mechanistic understanding of LSD1 inhibition in these settings.

Performance of these investigations may be conditional on the results of the clinical trial and samples may be selected for analysis on the basis of the clinical outcome. All samples will be retained for a maximum of 15 years after the last subject completes the study.

Details on sample collection, processing, storage and shipping procedures are provided in the SPM.

7.6.1. Biomarker Analysis

All subjects will be asked to submit peripheral blood samples at baseline, during the study, and at the end of treatment. All subjects will also be asked to submit fresh bone marrow aspirate at baseline and during the study. There is an optional bone marrow aspirate collection at the end of treatment. These samples will be used to conduct retrospective tests to understand the mechanistic activity of GSK2879552 alone and in combination with azacitidine, therapeutic response and the identification of potential markers of sensitivity or resistance through the assessment of DNA, RNA and/or protein. These studies may include but are not limited to DNA methylation, transcriptomic, and genomic analyses.

7.7. Genetics

A 2 mL saliva sample for DNA isolation will be collected from participants who have consented to participate in the genetics analysis component of the study. Participation is optional. Participants who do not wish to participate in the genetic research may still participate in the study.

In the event of DNA extraction failure, a replacement genetic saliva sample may be requested from the participant. Signed informed consent will be required to obtain a replacement sample unless it was included in the original consent.

See [Appendix 4](#) for Information regarding genetic research. Details on processes for collection and shipment and destruction of these samples can be found in the Time and Events Schedule (Section [7.1](#)).

8. DATA MANAGEMENT

For this study, data will be collected using defined electronic case report forms (eCRFs), transmitted electronically to GSK and combined with data provided from other sources in a validated data system.

Management of clinical data will be performed in accordance with applicable GSK standards and data cleaning procedures to ensure the integrity of the data, e.g. removing errors and inconsistencies in the data. AEs and concomitant medications terms will be coded using Medical Dictionary for Regulatory Activities (MedDRA) and an internal validated medication dictionary, GSK Drug. Electronic CRFs (eCRFs), including queries and audit trails, will be retained by GSK, and copies will be sent to the investigator to maintain as the investigator copy.

When laboratory samples (i.e., hematology and clinical chemistry) are analyzed by a central laboratory the results will be stored in a database maintained by the central laboratory and transferred to GSK at agreed times.

In all cases, subject initials will not be collected or transmitted to GSK according to GSK policy.

9. STATISTICAL CONSIDERATIONS AND DATA ANALYSES

9.1. Hypotheses

9.1.1. Part 1:

With respect to the primary objectives and endpoints, no specific statistical hypotheses are being tested. The primary focus will be on determining the recommended dose for further exploration, based upon the safety, PK and efficacy profiles of GSK2879552 plus azacitidine in subjects with relapsed/refractory HR MDS.

9.1.2. Part 2: Disease-Specific Expansion Cohorts

The primary goal of Part 2 is to evaluate disease-specific clinical activity in subjects with GSK2879552, alone or in combination with azacitidine, in adult subjects with MDS. Clinical activity is defined as a clinical benefit rate (% of subjects achieving CR, PR, HI or SD [per 2006 IWG criteria]). This will be conducted by testing the null hypothesis that $P_0 \leq 0.3$ versus the alternative that $P_1 \geq 0.5$, Subjects in Part 1 and Part 2 treated with the same starting dose will be analyzed together.

The Part 2 portion of the study will employ a Bayesian predictive adaptive design [Lee, 2008] for Arm A and Arm B separately that allows the trial to be monitored more frequently at multiple stages. The criteria will be based on a historically unimportant response rate of 30% versus a response rate of interest of 50%. Bayesian statistics will be employed to calculate the predictive probability that the response rate $\geq 50\%$ and $\geq 30\%$ at interim assuming a Beta prior for the Binomial distributed data. Predictive probability calculates the probability that the response rate $\geq 50\%$ or $\geq 30\%$ at the end of Part 2 given the responses that are currently being observed at interim. It predicts what is likely to happen at the end of Part 2 so it is more meaningful and straightforward than posterior probability. A weak prior Beta (0.005, 0.005) is used, which is equivalent to the information present in 0.01 subjects. The first interim analysis may be conducted when at least 10 subjects are recruited for each Arm. Futility interim analysis decision rules for the 10th to 28th evaluable subjects, specifying the number of subjects with clinical activity (CR, PR, HI or SD) needed for continuing enrolment or stopping for futility when total sample size is up to 28, is presented in Table 5. These rules are intended as a guideline. Actual decisions will depend on the totality of the data.

Table 5 Decision Making Criteria for Futility

| Number of Evaluable Subjects | ≤ This Number of Responses to Stop Early for Futility | Probability of continuing enrolling when CBR=0.3 | Probability of continuing enrolling when CBR=0.5 |
|------------------------------|---|--|--|
| 10 | 1 | 0.8507 | 0.9893 |
| 12 | 2 | 0.7363 | 0.9783 |
| 14 | 3 | 0.6242 | 0.9655 |
| 16 | 3 | 0.6242 | 0.9655 |
| 18 | 4 | 0.5739 | 0.9620 |
| 20 | 5 | 0.5087 | 0.9566 |
| 22 | 6 | 0.4414 | 0.9500 |
| 24 | 8 | 0.2601 | 0.9103 |
| 26 | 9 | 0.2059 | 0.8927 |
| 28 | 11 | 0.0000 | 0.0000 |

For the separate interim looks in each cohort in Part 2, the enrollment for that cohort may be stopped due to futility if the predictive probability that the confirmed response rate $\geq 30\%$ (historical control) is small (e.g., less than a 2% chance for a total sample size of 28 subjects). Enrollment may also be stopped due to futility if the equivalent of less than 2 responses is observed in the first 10 enrolled evaluable subjects in that cohort or less than 3 responses are observed in the first 12 evaluable subjects. The evaluable subject is defined as a subject, who has either progressed, withdrew from the study, was lost to follow-up, or is ongoing and has completed at least one post treatment disease assessment. For example, when there are 10 evaluable subjects available at the time of interim analysis with only one response, then the Arm may be stop for futility. Otherwise, the enrolment of the respective Arm will continue to the target sample size.

When the total sample size in a treatment arm is 28 and at least 12 responders out of 28 subjects are observed, we can claim null hypothesis is rejected.

No formal hypotheses are set up to compare the activity between Arm A and Arm B. The CBR and ORR will be reported for both arms separately at the end of Part 2.

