4.8. Type and Number of Subjects

Approximately 3-12 subjects may be enrolled in Part 1 of each Arm. Later, approximately 28 subjects will be enrolled in Part 2 of each Arm with a total of 74 (Arm A: 6+28; Arm B: 12+28) subjects in the study. The number of subjects may change depending on the dose levels in Part 1.

Additional subjects/cohorts may be enrolled to allow for evaluation of additional dose levels.

If subjects prematurely discontinue the study, additional replacement subjects may be recruited at the discretion of the Sponsor.

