6.3. Treatment Assignment

In Part 1, subjects will be assigned to Arm A (GSK2879552 only) or Arm B (GSK2879552 in combination with azacitidine) according to the investigator discretion and/or the availability of the enrolment slot.

In Part 2, subjects will be assigned to Arm A (GSK2879552 only) or Arm B (GSK2879552 in combination with azacitidine) in accordance with the randomization schedule generated by Clinical Statistics, prior to the start of the study, using validated internal software.

Subjects will be identified by a unique subject number that will remain consistent for the duration of the study.

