9.3.2.1. Part 2 Cohort Expansion

Interim data will be evaluated to monitor efficacy and safety. Enrollment may be stopped early for futility, should various criteria occur based on accrued data. The decision criteria for early stop for futility based on Bayesian Adaptive design are described in Section 9.1.2. The decision will be made for each individual cohort.

The study population used for decision-making at the interim analyses during Part 2 (Expansion Cohort) will be termed All Evaluable Subjects defined in Section 9.1.2. This will be the population for Bayesian adaptive design described in Section 9.1.2 and summaries of response if data warrant. Any evaluable subject from Part 1 of the study who has the same initial dose as in Part 2 will be included in this analysis. Because subjects enroll at different times, not all subjects will have been on the study long enough to have a single or multiple disease assessments. Since disease assessments are to be completed every 4 weeks, subjects who have at least one post-baseline disease assessment or have progressed or died or permanently withdraw from the study will be included in this population.

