9.4.1. Clinical Activity Analyses

The clinical benefit rate (CBR) is defined as the percentage of subjects with a Complete Remission (CR), marrow complete remission (mCR) or a Partial Remission (PR) or a Hematologic Improvement (HI) or Stable Disease (SD) at any time as per disease-specific criteria ([Appendix 5](#) and [Appendix 6](#)). Subjects with unknown or missing response will be treated as non-responders, i.e. these subjects will be included in the denominator when calculating the percentage. The number and types of responses, as outlined in IWG criteria [[Cheson, 2006](#)], will be listed and summarized separately, as appropriate.

The ORR will be reported at the interim and final analysis for each arm specified in Part 2 as well as all evaluable subjects in Part 1 treated at or above RP2D. Part 1 and Part 2 subjects who received the same dose within the same treatment arm may be combined together in the analysis. The estimates along with 95% exact confidence interval (CI) will be provided.

The CBR and ORR differences between the two cohorts will be provided along with corresponding 95% CI. A chi-square test will be used to test for differences between arms if data warrant.

Duration of response is defined as the subset of subjects who show a response (CR, mCR, PR, or HI), the time from first documented evidence of response until the first documented sign of disease progression or death. Duration of response will be summarized descriptively for each arm, if data warrant, using Kaplan-Meier medians and quartiles. Details on rules for censoring will be provided in the RAP.

For the analysis of **Progression-free survival (PFS)**, if the subject received subsequent anti-cancer therapy prior to the date of documented events, PFS will be censored at the last adequate assessment (e.g. assessment where visit level response is CR, mCR, PR, HI or SD) prior to the initiation of therapy. Progressive disease (PD) will also be defined per standard criteria. Otherwise, if the subject does not have a documented date of events, PFS will be censored at the date of the last adequate assessment. Further details on rules for censoring will be provided in the RAP. PFS will be summarized by arm and dose using Kaplan-Meier quantile estimates along with 2-sided 95% CIs at the time of final analysis, if data warrant.

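### Part 1 subjects must be pooled into the Part 2 test, but the futility table, the 12-of-28 rule and the stated alpha and power apply only to 28 subjects per arm

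*Protocol*

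**What the plan says.** **Pooling.** In the paragraph that sets up the Part 2 hypothesis test, section 9.1.2 states: "Subjects in Part 1 and Part 2 treated with the same starting dose will be analyzed together". Section 9.3.2.1, defining the interim decision population, states: "Any evaluable subject from Part 1 of the study who has the same initial dose as in Part 2 will be included". Both use *will*. Section 9.4, section 9.4.1 and the Analysis part of the synopsis say only that data from the two parts *may* be combined.

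**Numbers.** Section 4.8 plans about 28 subjects in Part 2 of each arm, "with a total of 74 (Arm A: 6+28; Arm B: 12+28) subjects in the study". Section 9.2.1 caps each expansion cohort at 28, giving 56 randomised 1:1. Part 1 of Arm A treats about 3-6 subjects at 2 mg (section 4.3.1). Part 1 of Arm B takes up to six per dose level, and Table 1 lets a lower cohort grow to 12 once the tolerated dose has been exceeded (section 4.3.2).

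**Decision rules.** Table 5 runs from 10 to 28 evaluable subjects and is called a guideline. The only success rule is that when the arm totals 28 and "at least 12 responders out of 28 subjects are observed, we can claim null hypothesis is rejected". Section 9.2.1 gives alpha 0.099 and 81% power for a maximum of 28.

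**Arm comparison.** Section 9.4.1 says the CBR and ORR differences will be given with 95% confidence intervals, and adds: "A chi-square test will be used to test for differences between arms if data warrant". Section 9.1.2 sets no formal between-arm hypothesis. In Part 1, subjects go to an arm "according to the investigator discretion and/or the availability of the enrolment slot" (section 6.3).

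**The concern.** The analysis set that the protocol requires differs from the set for which its decision rule was built. If 28 subjects are randomised to an arm and any Part 1 subject at the same starting dose joins them, the total passes 28. The protocol then has no rejection threshold, and its stated error rates describe a different design. In an open-label trial, a threshold chosen once responses are known would not be credible.

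Pooling also moves the looks. With 6 Part 1 subjects in the set, the 10-subject look falls after 10 - 6 = 4 Part 2 subjects.

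A smaller issue is the between-arm difference. Nothing limits it to randomised subjects, so optional pooling could bring in subjects whose arm was not assigned by chance.

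**Working it through.** **Inputs.** Null CBR 0.30 and target 0.50 (section 9.1.2). Table 5: stop at or below 1/10, 2/12, 3/14, 3/16, 4/18, 5/20, 6/22, 8/24, 9/26. Success at 12 or more of 28. Part 1 subjects at the Part 2 dose: 3 to 6, so N = 28 + 3 = 31 to 28 + 6 = 34.

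**Method.** Let f_n(k) be the probability of k responders among the first n subjects without having stopped. Then f_n(k) = (1 - p) f_{n-1}(k) + p f_{n-1}(k - 1). At each look, f_n(k) is set to 0 for k at or below the boundary. The probability of rejection is the sum of f_N(k) over k at or above the threshold.

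**Step 1: the plan's own figures, N = 28, threshold 12.**
- All continuation probabilities for looks 10 to 26 match Table 5 to four decimals (for example 0.8507 and 0.9893 at 10; 0.2059 and 0.8927 at 26).
- Alpha 0.0991 (stated 0.099); power 0.8174 (stated 81%).
- Total probability of not rejecting: 0.901 at p = 0.3 and 0.183 at p = 0.5 (stated 0.90 and 0.183).
- Without looks: alpha 0.1028, power 0.8275.

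The stated figures therefore belong to a 28-subject set with the looks followed.

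**Step 2: keep a count of 12 in the pooled set.**

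| N | Alpha, looks followed | Power, looks followed | Alpha, looks not followed |
|---|---|---|---|
| 31 | 0.151 | 0.877 | 0.192 |
| 34 | 0.181 | 0.890 | 0.307 |

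The last column is P(X >= 12) for a binomial with N subjects and p = 0.3. It is an upper limit, relevant only because the looks are non-binding.

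**Step 3: scale the threshold as 12/28.** 31 x 12/28 = 13.3, so 14; 34 x 12/28 = 14.6, so 15. With looks followed:
- 14 of 31: alpha 0.052, power 0.754.
- 15 of 34: alpha 0.053, power 0.786.

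**Step 4: smallest threshold that keeps alpha at or below about 0.099, looks at 10 to 26 unchanged.**

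| N | Threshold | Alpha | Power |
|---|---|---|---|
| 31 | 13 | 0.097 | 0.836 |
| 32 | 14 | 0.065 | 0.795 |
| 33 | 14 | 0.080 | 0.826 |
| 34 | 14 | 0.094 | 0.848 |

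**The case against.** **The rule is conditional on 28.** The protocol never says to apply a count of 12 to a larger set, so an inflated alpha is not something it prescribes. That is right. Step 3 shows that another natural reading makes the test stricter, so the direction of the error is not determined. What stands is that no rule exists above 28.

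**28 could mean the pooled total.** If the decision set closed at the 28th pooled evaluable subject, alpha would stay at 0.0991. But this contradicts 28 newly enrolled per expansion cohort, 56 randomised, and the 6+28 and 12+28 breakdown, and it leaves 3 to 6 treated subjects outside the test.

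**Stronger readings that the documents do not support:**
- *N = 40, with alpha 0.559.* This needs 12 Part 1 subjects at the Part 2 dose. Section 4.3.2 takes up to six per level. Growth to 12 arises only after another dose has proved too toxic, so it would exceed the planned 12 in Part 1 of Arm B. The 0.559 also ignores every look; with looks it is 0.202.
- *A third pooling rule at or above the RP2D.* In section 9.4.1 that phrase says which Part 1 subjects have ORR reported alongside Part 2. It does not pool them. The real inconsistency is *will* against *may*.
- *An invalid between-arm test.* The comparison is descriptive, pooling there is optional, and the chi-square test is conditional. Only a clarification is needed.
- *Pooled responses biased by dose selection.* Section 9.1.1 does say the dose is chosen "based upon the safety, PK and efficacy profiles of GSK2879552 plus azacitidine", but that names only the combination. Section 4.3.1 confirms the Arm A dose on DLTs, and section 4.3.2 cites PK and safety for the RP2D. This is too thin to carry weight.

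**Conclusion.** The point holds for the decision rule. As written, a fully enrolled arm has about 31 to 34 subjects in its mandated analysis set, and neither the success threshold nor the stated alpha of 0.099 and power of 81% applies to it. Depending on the reading, alpha runs from about 0.05 (with power below 0.80) to 0.181 with the looks followed, or up to 0.307 if they are not.

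This assumes that the arm reaches 28 in Part 2, that 3 to 6 Part 1 subjects had the same starting dose, and that responses are independent with a common rate. An arm stopped for futility would be smaller. The separate reporting and analysis plan is not at hand. A threshold given there would fill the gap, but the protocol's pooling sentences and stated error rates would still need to agree with it.

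**What to change.** **Preferred.** State in sections 9.1.2 and 9.3.2.1 that Table 5 and the 12-of-28 rule apply to the 28 randomised Part 2 subjects per arm (alpha 0.099, power 0.817). Report pooled Part 1 and Part 2 results at the same dose as supportive, without the decision rule. Planned enrolment is unchanged. The cost is that the first futility look comes 3 to 6 subjects later in Part 2.

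**Alternative.** Keep the pooling and give the threshold for each possible final N, using Step 4: for example 13 of 31 and 14 of 34. Restate alpha and power accordingly. Note that N = 32 falls slightly short of 81% power.

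**Either way:**
- Use one wording on pooling throughout, reconciling the mandatory text in sections 9.1.2 and 9.3.2.1 with the optional text in the synopsis and sections 9.4 and 9.4.1.
- Add a line to section 9.4.1 that the CBR and ORR differences between arms use randomised Part 2 subjects only.

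The changes are to wording, and should be made before the first Part 2 look.

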2.2.6. Azacitidine

Azacitidine (5-azacitidine, 5-aza, Vidaza) is a pyrimidine nucleoside analog of cytidine, which causes hypomethylation (demethylation) of DNA and has direct cytotoxicity on abnormal bone marrow hematopoietic cells. It is approved for the treatment of patients with MDS in the US. Available studies indicate overall response rates in patients with low or intermediate-1 risk MDS of approximately 50 percent, with survival benefits observed in responders versus nonresponders. In most centers azacitidine is administered in an outpatient setting at a dose of 75mg/m² per day subcutaneously for 7 consecutive days every 28 days. Best responses may not occur until six cycles have been given. In the combined the Cancer and Leukemia Group B (CALGB) experience, the median number of cycles to first response was three, with 90 percent of responses seen by cycle six. More convenient dosing regimens, in which the agent is given for only five consecutive days, or with a "drug holiday" over the weekend, or as a 10-day cycle have also been adopted by clinicians. Dose adjustment and growth factor support are necessary for some patients during treatment with azacitidine.

Most common adverse reactions (>30%) by SC route are: nausea, anemia, thrombocytopenia, vomiting, pyrexia, leukopenia, diarrhea, injection site erythema, constipation, neutropenia and ecchymosis. Most common adverse reactions by IV route also included petechiae, rigors, weakness and hypokalemia. Azacitidine is available in lyophilized powder in 100 mg single-use vials.

Azacitidine is rapidly absorbed and eliminated after SC administration with the peak plasma azacitidine concentration occurring in 0.5 hour and a mean half-life of 41 minutes. The bioavailability of SC azacitidine relative to IV azacitidine is approximately 89%, based on AUC. AUC and C_{max} of SC administration of azacitidine were approximately dose proportional within the 25 to 100 mg/m² dose range. Multiple dosing at the recommended dose-regimen does not result in drug accumulation. Urinary excretion is the primary route of elimination of azacitidine and its metabolites [[Vidaza Prescribing Information 2015](#)].

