12.10. Appendix 10: IWG CRITERIA FOR RESPONSE

| Category | Response Criteria |
|------------------------------|--|
| Complete Remission | Bone marrow: $\leq 5\%$ myeloblasts with normal maturation of all cell linesa Persistent dysplasia will be noteda,b Peripheral blood (Response must be maintained for at least 4 weeks) Hgb ≥ 11 g/dL Platelets ≥ 100 Gi/L Neutrophils ≥ 1.0 Gi/Lb Blasts 0% |
| Partial Remission | All CR criteria if abnormal before treatment except: Bone marrow blasts decreased by $\geq 50\%$ over pre-treatment but still $> 5\%$ Cellularity and morphology not relevant |
| Marrow CR^b | Bone marrow: $\leq 5\%$ myeloblasts and decrease by $\geq 50\%$ over pre-treatment ^b Peripheral blood: if HI responses, they will be noted in addition to marrow CR ^b |
| HI | Erythroid (HI-E): hgb increase of > 1.5 g/dL decrease of $>$ RBC transfusions/8weeks versus pretreatment requirement in previous 8 weeks; only RBC transfusions given for a pretreatment Hgb of < 9.0 g/dL count Platelet (HI-P): increase of $> 30,000$ /mL (starting with $> 20,000$ /mL) increase from $< 20,000$ /mL to $> 20,000$ /mL by $> 100\%$ Neutrophil (HI-N): increase of $> 100\%$ and > 500 /uL |
| Stable Disease | Failure to achieve at least PR, but no evidence of progression > 8 wks |
| Disease Progression | For subjects with: 
 • Less than 5% BM blasts: $\geq 50\%$ increase in blasts to $> 5\%$ blasts • 5%-<10% BM blasts: $\geq 50\%$ increase to $> 10\%$ blasts • 10%-<20% BM blasts: $\geq 50\%$ increase to $> 20\%$ blasts • 20%-30% BM blasts: $\geq 50\%$ increase to $> 30\%$ blasts Any of the following: 
 • At least 50% decrement from maximum remission/response in granulocytes or platelets • Reduction in Hgb by ≥ 2 g/dL • Transfusion dependence |
| Non-evaluable | Subject does not meet any of the above criteria |

BM = bone marrow ; CR = complete remission; Hgb = hemoglobin;; PR = partial remission

a. Dysplastic changes should consider the normal range of dysplastic changes (modification).

b. Modification to IWG response criteria [[Cheson, 2006](#)].

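### The interim futility looks count a subject as evaluable after one 4-week assessment, although stable disease, which counts as a success, cannot be determined until after 8 weeks.

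*Protocol*

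**What the plan says.** - **Endpoint at the looks.** Protocol section 9.1.2 introduces Table 5 as "specifying the number of subjects with clinical activity (CR, PR, HI or SD) needed for continuing enrolment or stopping for futility". SD is therefore a success at every look.
- **Who is counted.** The same section makes a subject evaluable on progression, withdrawal or loss to follow-up, "or is ongoing and has completed at least one post treatment disease assessment". Section 9.3.2.1 repeats the rule and gives the interval: "Since disease assessments are to be completed every 4 weeks, subjects who have at least one post-baseline disease assessment" belong to the interim population, together with those who have progressed, died or permanently withdrawn.
- **What SD requires.** Appendix 10 (section 12.10) defines it as "Failure to achieve at least PR, but no evidence of progression > 8 wks". A subject who fits no listed category is non-evaluable there.
- **Unknown response.** Section 9.4.1 keeps subjects with unknown or missing response in the denominator as non-responders. No rule is given for a subject whose SD is still pending at an interim look.
- **Status of the rules.** Section 9.1.2 calls the boundaries a guideline and leaves decisions to the totality of the data. Sections 9.1.2 and 9.3.2.1 include same-dose Part 1 subjects in the analysis.

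**The concern.** The protocol itself fixes the endpoint, the evaluable set, the SD duration and the stopping boundaries, and they do not fit together. An ongoing subject at week 4 without CR, mCR, PR or HI is evaluable under 9.1.2, but fits no category in Appendix 10.

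Entry to the denominator also depends on outcome. Progressors and drop-outs enter as soon as they fail, whereas an SD success cannot be recognised for more than 8 weeks. Table 5 and the stated power treat every counted subject as having a final status. If pending subjects score zero, an active arm is more likely to fall at or below a boundary. If they score as SD, the interim rate includes successes that may be reversed by the next visit, and an inactive arm is stopped too rarely.

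**Working it through.** **Inputs from the protocol.** Null rate 0.30 and target rate 0.50 (9.1.2). Looks at n = 10, 12, 14, 16, 18, 20, 22, 24, 26, 28, stopping at ≤ 1, 2, 3, 3, 4, 5, 6, 8, 9, 11 (Table 5). Success is 12 or more of 28 (9.1.2). Assessments are every 4 weeks (9.3.2.1). SD requires more than 8 weeks (Appendix 10).

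**Step 1: reproduce the plan.** An exact binomial recursion over these looks matches every Table 5 continuation value from n=10 to n=26 to four decimals, at both rates. It gives type I error 0.0991 (stated 0.099) and power 0.8174 (stated 81%). At rate 0.5 the chance of stopping before n=28 is 1 − 0.8927 = 0.107. The 0.183 in section 9.2.1 is 1 − 0.817 and so includes failing at n=28. The comparator below is 0.107. The stated figures are thus those of the design when every counted status is final.

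**Step 2: how many subjects might be pending.** The protocol gives no accrual rate. Assume 28 per arm over 9 to 18 months. With 4 weeks ≈ 0.92 months, the number between week 4 and week 8 at a given time is about 28/18 × 0.92 = 1.4 to 28/9 × 0.92 = 2.9. Hence u = 1 to 3 pending subjects per look.

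**Step 3: first look, exact, all benefit SD.** With u of the 10 scored zero, X is Binomial(10 − u, 0.5) and P(X ≤ 1) = (1 + (10 − u)) / 2^(10 − u).

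| u | P(stop at n=10) |
|---|---|
| 0 | 11/1024 = 0.011 |
| 1 | 10/512 = 0.020 |
| 2 | 9/256 = 0.035 |
| 3 | 8/128 = 0.063 |

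**Step 4: all looks, true rate 0.5.** Simulation on the Table 5 boundaries, with the last u subjects at each look unable to count as SD. Every boundary crossing is treated as a stop. Final success needs 12 of 28 with complete status.

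| u | Stop before 28, all benefit SD | Power | Stop before 28, half SD | Power |
|---|---|---|---|---|
| 0 | 0.107 | 0.817 | 0.107 | 0.817 |
| 1 | 0.15 | 0.80 | 0.13 | 0.81 |
| 2 | 0.20 | 0.76 | 0.16 | 0.79 |
| 3 | 0.27 | 0.70 | 0.19 | 0.77 |

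In the half-SD columns, the other half of the benefit is assumed visible at week 4. The model does not include the earlier entry of progressors and drop-outs, which acts in the same direction.

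**Step 5: which visit can establish SD.** Cycle 3 Day 1 falls 2 × 28 = 56 days after first dose. With the ±3-day window (section 7) that is day 53 to 59, so it does not reliably exceed 8 weeks. Cycle 4 Day 1 falls at 84 ± 3 days and always does.

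**The case against.** **The direction is not fixed by the text.** This stands. No sentence says that a pending subject scores zero at an interim look. The non-responder rule in 9.4.1 is written for unknown or missing response, and the PFS paragraph there mentions SD as a visit-level response. If week-4 non-progression were called SD, the bias would reverse. A reader might infer that the plan necessarily leads to false stops. It does so only on the non-responder reading. The other reading contradicts Appendix 10, so neither leaves Table 5 valid.

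**The boundaries are non-binding.** This also stands. In an open-label study the team can see who is pending, so the stop rates above are those of following the guideline strictly. The stated error rates, however, are also those of following it, and section 9.1.2 gives one response in 10 as an example of when an arm may stop.

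**The first look may be less exposed.** Part 2 opens only after Part 1 is complete in both arms, so same-dose Part 1 subjects may already have a final status. Later looks are not protected in this way.

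**Two stronger inferences do not hold.**

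- Section 2.2.6 says that for azacitidine "the median number of cycles to first response was three, with 90 percent of responses seen by cycle six". A reader might conclude that the combination arm suffers most. But SD already counts as success, so a late responder without progression counts once SD is established. That experience is also general, whereas all subjects here have failed a hypomethylating agent.
- The sentence "The first interim analysis may be conducted when at least 10 subjects are recruited for each Arm" might seem to conflict with the 10 evaluable subjects required in 9.2.1. Ten recruited is a looser condition and compatible with it.

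**Conclusion.** The mismatch is in the protocol's own wording: one 4-week assessment makes an ongoing subject evaluable, but SD needs more than 8 weeks. As written, Table 5 and the 81% power do not describe the interim rule.

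If pending subjects count as non-responders and the guideline is followed, 1 to 3 pending subjects per look raise the chance of stopping an arm with a true rate of 0.5 before n=28 from 0.107 to between 0.13 and 0.27. Power falls from 0.817 to between 0.81 and 0.70. The lower end has one pending subject and half the benefit as SD; the upper end has three and all of it as SD. Accrual rate and SD share are assumptions, so the size is a range. The loss is modest at the lower end and material at the upper end. It should be corrected before the first look.

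**What to change.** In sections 9.1.2 and 9.3.2.1, define the set for each look by time since first dose: the first n consecutive subjects dosed long enough ago to have had a scheduled assessment more than 8 weeks after first dose, whatever their outcome. Progressors and drop-outs then enter on the same clock as everyone else, and Table 5 applies again (0.107 and 0.817 at a true rate of 0.5).

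State which visit establishes SD. Cycle 3 Day 1 does not reliably exceed 8 weeks, so either use the next 4-weekly assessment (Cycle 4 Day 1), or reconcile the SD duration wording in Appendix 10 with the visit schedule.

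The change is to wording only. Each look comes about 4 weeks later (if SD is settled at Cycle 3 Day 1 after reconciliation) to 8 weeks later (Cycle 4 Day 1). At the assumed 1.4 to 2.9 subjects per 4 weeks, that is about 1 to 3 more subjects per arm enrolled before a true futility stop in the first case, and about 3 to 6 (twice as many) in the second.
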